7.2.7 Subgroup Analysis

The primary efficacy variable (change from baseline in number of binge days per week at Week 12) and key secondary variable (change from baseline in BE-CGI-S at Week 12) will be examined to explore the consistency of the treatment effect across certain subgroups listed below (if there are at least 45 subjects in the subgroup).

The subgroup analysis will be conducted based on a similar MMRM model to the corresponding primary efficacy analysis with three additional terms: subgroup, treatment-by-subgroup interaction, and 3-way interaction of treatment*subgroup*visit.

Descriptive statistics (N, mean, standard deviation), LS Means and SE, the treatment differences vs. placebo and 95% CIs at Week 12 from the MMRM model will be provided for each category of the subgroups by treatment group:

- Gender: male or female
- Race group: White, Non-white
- Age group: <40, \geq 40 years old
- Ethnicity: Hispanic, non-Hispanic
- Baseline BMI (kg/m^2): Non-obese (<30), Obese (\geq 30 kg/m^2)
- Baseline severity (number of episodes/week): Moderate (\leq 7), Severe ($>$ 7)

P-value for treatment-by-subgroup interaction at Week 12 from the MMRM model will be provided. For each category of above subgroups and for overall subjects, LS mean differences (vs. placebo) and their 95% CIs in the change from baseline at week 12 in the number of binge

321

days/week will be plotted on a same forest plot. A similar forest plot will be provided for BE-CGI-S as well.

All subgroup analyses will be based on the ITT population.

7.3 Pharmacokinetics (PK) Analysis

Plasma concentrations for dasotraline will be summarized at Week 2, 6, and 12 by the most recent dasotraline dose level for the PK population. The descriptive statistics (n, mean, SD, coefficient of variation [CV%], median, range) will be provided by most recent dasotraline dose group. A listing of PK concentration for all samples will be provided.

7.4 Safety

7.4.1 Analysis Specifications

Safety reporting includes all safety data reported during the 12-weeks double-blind treatment period, as well as the all safety data reported in post-treatment withdrawal period, if a subject does not enter the extension study.

The safety data will be analyzed by treatment group based on the safety population for data up to the end of treatment period and on the withdrawal population for data collected during the withdrawal period, separately, as appropriate. Specifically, the data, which are used to assess physical dependence and withdrawal symptoms, will be analyzed by treatment for data collected in the withdrawal period based on the modified withdrawal population for AE, CSSA and DESS, and based on withdrawal population for MADRS and HAM-A, respectively. Unless otherwise specified, for continuous data collected in the treatment period, the actual value and change from baseline (ie, DB baseline) will be summarized by treatment and visit; for continuous data collected in the withdrawal period, the actual value, change from DB baseline (when applicable), and change from withdrawal baseline will be summarized by treatment and visit.

There will be no imputation of missing values for clinical laboratory test results, vital sign measurements, and ECG evaluations in the by-visit analyses. All analyses of safety data are descriptive. No inferential analyses of safety data are performed.

7.4.2 Adverse Events

All AEs are coded using Medical Dictionary for Regulatory Activities (MedDRA) version 18.0 or higher.

Treatment-Emergent Adverse Event (TEAE)

A treatment-emergent adverse event (TEAE) is defined as an AE with a start date on or after the date of first dose through 7 days after study drug discontinuation (14 days for serious adverse events and deaths) for subjects who complete or discontinue this study but do not enter into the extension study), or through the last study day of the double-blind treatment period for subjects

continuing into the extension study (ie, subjects in safety population). AEs with a start date prior to initiation of double-blind study medication which are reported to have an increase in intensity, or which are reported to have a attribution in relationship to study medication (ie, attribution to possible related, probably related, related) after the initiation of double-blind study medication are considered as TEAEs.

Discontinuation-emergent adverse event (DEAE) is defined as an AE with a start date after the last dose day of study medication through the last study visit in the withdrawal period.

Table summary of overall AEs (and SAEs) will be limited to TEAEs and DEAEs. All AE data will be displayed in data listings. For sake of simplicity, hereafter TEAE is referred as AE in this section.

The overall incidence (ie, number and percent of subjects with one or more AE in each category) of AEs, serious AEs, deaths, AEs leading to discontinuation, study drug-related AEs, serious study drug-related AEs, study drug-related AEs leading to discontinuation, and serious AEs leading to discontinuation, serious study drug-related AEs, will be summarized by treatment group.

The AEs also will be summarized by system organ class (SOC) and preferred term (PT) by presenting the number and percentage of subjects with each AE category. The incidence of AEs (by preferred term, grouped by SOC, and presented by treatment group) will also be summarized by severity, by the relationship to study medication, by the action taken regarding the study medication, as well as by the outcome. If a subject has the same AE on multiple occasions, the highest severity (severe, moderate, mild) recorded for the event and the highest drug relationship (unrelated, unlikely to be related, possibly related, probably related, and definitely related) will be presented, respectively. The relationship to study medication will be presented by 2 categories: related (which includes possibly related, probably related, and related, as determined by investigators), and not related (which includes unrelated and unlikely to be related, as determined by investigators). Furthermore, for AE summary by SOC and PT or PT only, the following combined preferred terms will be summarized as well:

- Insomnia: Insomnia, Initial insomnia, Middle insomnia, Terminal insomnia.
- Hallucination: Hallucination; Hallucination, auditory; Hallucination, gustatory; Hallucination, olfactory; Hallucination, synaesthetic; Hallucination, tactile; Hallucination, visual; Hallucinations, mixed; Hypnagogic hallucination; Hypnopompic hallucination; Somatic hallucination.

A Kaplan-Meier plot of the time to the first onset of treatment emergent insomnia (combined term) will be presented by treatment group. Time to the first onset (in days) is defined as the earliest onset date of insomnia – start date of DB treatment period + 1. Subjects who do not experience any insomnia on or before the last dose date will be censored on the day of last dose.

321

Prevalence rate of insomnia (combined term) at a study day in the DB treatment period is defined as number of subjects experiencing insomnia on the day divided by number of subjects remaining on DB treatment period at that time point. It is notable that subjects may experience multiple insomnia episodes during the study. Prevalence rate over time will be presented graphically by treatment group.

AE maximum relationship

Each AE will be classified as ‘related’, ‘not related’, and ‘not specified’. TEAEs with a missing AE relationship will be classified as ‘not specified’. AE summary by the relationship to the study medication will be based on the highest relationship within an SOC and PT. Response values will be ranked in order from minimum to maximum as ‘not specified’ < ‘not related’ < ‘related’.

AE maximum severity

AEs with a missing severity will be classified as ‘not specified’. AE summary by the severity will be based on the maximum severity within an SOC and PT. Response severity values will be ranked in order from minimum to maximum as ‘not specified’ < ‘mild’ < ‘moderate’ < ‘severe’.

AE maximum action taken

AEs with a missing action taken will be classified as ‘unknown’. AE summary by the action taken will be based on the maximum action taken within an SOC and PT. Response action values will be ranked in order from minimum to maximum as ‘not applicable’ < ‘unknown’ < ‘dose increased’ < ‘unchanged’ < ‘dose reduced’ < ‘drug interrupted’ < ‘drug withdrawn’.

AE maximum outcome

AEs with a missing outcome will be classified as ‘unknown’. AE summary by the outcome will be based on the maximum outcome within an SOC and PT. Response outcome values will be ranked in order from minimum to maximum as ‘unknown’ < ‘recovered/resolved’ < ‘recovered/resolved with sequelae’ < ‘recovering/resolving’ < ‘not recovered/not resolved’ < ‘fatal’.

AEs with Special Interest

A list of preferred terms that are to be combined for the assessment of each of the pre-specified adverse events (including cardiovascular-related AEs, metabolic related AEs, neuropsychiatric-related AEs, and suicide and self-injury related AEs) is provided in [Attachment 9.4](#). These AE preferred terms are determined and verified by medical review of coded AE terms during BDRM and finalized prior to database lock. The incidence of cardiovascular-related AEs, metabolic related AEs (weight-related and non-weight-related), neuropsychiatric-related AEs (including a defined subset of psychosis and mania-related AEs) and suicide and self-injury related AEs will be summarized by treatment, respectively.

Listings will also be generated for deaths, SAEs, and discontinuations due to AEs. All adverse events regardless of treatment emergent status will be provided in the AE data listing.

Discontinuation-Emergent Adverse Event (DEAE) (ie, AEs Onset After Last Study Dose)

All summary of DEAEs will be based on a ‘modified’ withdrawal population (see Section [6.1.7](#)).

The overall incidence of DEAEs, DEAEs by SOC and PT (by presenting the number and percentage of subjects with each AE category), and DEAEs by PT will be summarized by treatment group.

In addition, incidence of DEAEs by SOC and PT will be also summarized using time intervals beginning with the earliest AE concurrent withdrawal duration in the withdrawal period, where denominators in percentage calculation for withdrawal duration intervals (in days) will be based on the number of subjects whose withdrawal duration are no less than the first day of the interval. Withdrawal duration (in days) will be derived as the last withdrawal visit date minus the last dose date +1 and withdrawal duration categories to be assessed are 1-7 days, 8-14 days, and ≥ 15 days.

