12.1.2. Serious Adverse Events

A serious adverse event (SAE) is an AE that meets one or more of the following criteria:

- Results in death.
- Is life-threatening.
- Requires hospitalization or prolongation of existing hospitalization.
- Results in persistent or significant disability or incapacity.
- Is a congenital anomaly or birth defect.
- Is an important medical event that may jeopardize the subject or may require a medical or surgical intervention to prevent one of the outcomes listed above. Examples of such medical events include allergic bronchospasm requiring intensive treatment in an emergency room or at home, blood dyscrasias or convulsions that do not result in inpatient hospitalization.

The term “severe” is often used to describe the severity of a specific event (as in mild, moderate, or severe myocardial infarction) (see [Section 12.3](#)); the event itself, however, may be of relatively minor medical significance (such as severe headache). This is not the same as

“serious,” which is based on subject/event outcome or action criteria usually associated with events that pose a threat to a subject's life or functioning as defined by the criteria above.

During the study, if a subject has a hospitalization or procedure (eg, elective surgery) that was scheduled before the study entry, ie, before informed consent for an event/condition that occurred before the study, the hospitalization is considered a therapeutic intervention and not the result of a SAE. However, if the event/condition worsens during the study, it should be reported as an AE (or SAE, if the event/condition results in a serious outcome such as prolongation of hospitalization).

Life-threatening means that the subject was, in the view of the Investigator, at immediate risk of death from the event as it occurred. This definition does not include an event that had it occurred in a more severe form might have caused death.

SAE criteria information will be captured on the case report form (CRF).

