12.4.1. Serious Adverse Event

If the Investigator or study center staff becomes aware of a SAE that occurs in a study subject after first administration of study drug through 30 days following the last dose of the study medication, this must be reported within 24 hours to PPD-PVG, the medical monitor, and Sunovion responsible physician whether considered related or unrelated to the study drug. SAEs must be recorded on the CRF and the data recorded should agree with that on the SAE form.

Following the end of subject participation in the study, the Investigator or an authorized delegate should report SAEs “spontaneously” to the PPD-PVG if considered at least possibly related to the study drug.

SAEs will be followed until resolution, loss to follow-up, stabilization of condition, or the event is otherwise explained.

In addition to the initial telephone notification, an initial SAE form as applicable must be completed and signed and sent via fax or email (see [Table 1](#)) to PPD-PVG within 1 business day of the Investigator or study center staff becoming aware of the event. The SAE form must be signed by the Investigator or appropriate designee. The Sponsor provides the SAE form used to report SAEs.

The Sponsor or designee will promptly notify all study centers and Investigators of a SAE that is determined to be expedited to the Regulatory Authorities in accordance with applicable law(s) and regulation(s). These SAEs must be promptly reported to the Institutional Review Board (IRB) by the Investigator or the appropriate person at the study center if required per IRB guidelines.

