15.4.2.1. Adverse Events

All AEs will be coded using Medical Dictionary for Regulatory Activities (MedDRA) version 18.0 or higher.

The terms used in the CRFs by Investigators to identify adverse events.

An adverse event (AE) is defined as having a start date on or after the date of first dose through 7 days after study drug discontinuation (14 days for serious adverse events and deaths) for subjects who complete or discontinue this study but do not enter into the extension study), or through the last study day of the double-blind treatment period for subjects continuing into the extension study.

A discontinuation-emergent adverse event (DEAE) is defined as an AE with a start date after the date of last dose of study drug through the last study visit in the withdrawal period for subjects who either complete the 12-week treatment period but do not enter into the extension study, or for subjects who are terminated early in the treatment period.

The summary of overall AEs (and SAEs) will be limited to AEs and DEAEs.

The overall incidence (ie, number and percent of subjects with one or more AE in each category) of AEs, serious AEs, deaths, AEs leading to discontinuation, study drug-related AEs, serious study drug-related AEs, study drug-related AEs leading to discontinuation, and serious AEs leading to discontinuation, serious study drug-related AEs, will be summarized by treatment group.

The AEs also will be summarized by system organ class (SOC) and preferred term (PT) by presenting the number and percentage of subjects with each AE category. The incidence of AEs (by PT, grouped by SOC, and presented by treatment group) also will be summarized by severity, by the relationship to study medication, by the action taken regarding the study medication, as well as by the outcome.

The overall incidence of DEAEs and serious DEAEs will be summarized by treatment group. The DEAEs also will be summarized by SOC and PT by presenting the number and percentage of subjects with each AE category.

The incidence of AEs of special interest, including but not limited to neuropsychiatric-related and cardiovascular-related AEs, will be summarized by treatment group.

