6.1.1.2. Withdrawal Period (Off Treatment)

For subjects who either are early terminated from DB period or complete DB period but do not enter the extension, withdrawal period analyses will be generated; no withdrawal period analyses will be produced for subjects entering the extension study.

The withdrawal period will begin with immediately after the last study dose. Study day relative to the last study dose date will be denoted as Day 0. The end of the withdrawal period is defined as the maximum of last study visit (scheduled or unscheduled) and last phone contact after the

321

last study dose. If the last study dose date is missing (eg, lost follow-up subjects), start and end days will be set as missing.

Each subject’s assessment at each visit (site or phone contact) in the withdrawal period will be assigned a study day with respect to start date of the withdrawal period.

- Study Day = Assessment date – start date of the withdrawal period if assessment date \geq start date of the withdrawal period

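### For subjects not entering the extension, SAEs and deaths are collected to 30 days after the last dose but counted by arm only to Day 14 or the last withdrawal visit, and the withdrawal-interval denominators are one day out

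*SAP*

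**What the plan says.** In what follows, Day n means n days after the last dose.

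- **Collection.** Protocol 12.4.1 requires 24-hour reporting of any SAE that "occurs in a study subject after first administration of study drug through 30 days following the last dose of the study medication", related or not. The same section adds: "SAEs must be recorded on the CRF and the data recorded should agree with that on the SAE form". The first SAE criterion in protocol 12.1.2 is "Results in death", so deaths fall under the 30-day rule. Non-serious AEs are collected only to the last study visit (protocol 12.1.1).
- **Treatment-emergent window.** For subjects not entering the extension, protocol 15.4.2.1 counts events "through 7 days after study drug discontinuation (14 days for serious adverse events and deaths". SAP 6.1.11.4.1 and 7.4.2 repeat this.
- **Discontinuation-emergent (DEAE) window.** Protocol 15.4.2.1 and SAP 7.4.2 start it after the last dose and end it at the final withdrawal-period visit. Protocol 11.8.10 plans that visit at Day 21 ± 1.
- **Tables.** SAP 7.4.2: "Table summary of overall AEs (and SAEs) will be limited to TEAEs and DEAEs". The section then uses AE to mean TEAE, so its by-arm table of serious AEs and deaths is a TEAE table. Protocol 15.4.2.1 also plans by-arm incidence of serious DEAEs. The DEAE tables named in the SAP are overall, by SOC and PT, and by PT. SAP Section 4 reports no change from the protocol's planned analyses.
- **Withdrawal intervals.** SAP 7.4.2: "Withdrawal duration (in days) will be derived as the last withdrawal visit date minus the last dose date +1". The intervals are 1–7, 8–14 and ≥15 days, and a subject is in a denominator if duration reaches the interval's first day. SAP 6.1.1.2: "Study day relative to the last study dose date will be denoted as Day 0".

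**The concern.** The plan collects a class of serious event and then defines its tables so that part of that class has no place in them. An unrelated SAE on Day 25 in a subject whose last contact was Day 21 goes on the CRF and into the listings, but into no arm's numerator. So does a death on Day 20 in a subject who declined withdrawal follow-up. The uncounted span is longest for early leavers without follow-up, whose numbers may differ between arms.

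The interval tables raise a second, smaller problem. Denominators sit on a scale one day ahead of the rest of the withdrawal analyses, and the planned visits fall where that day matters. Late-interval DEAE incidence, which bears on the withdrawal-effects objective, would be understated.

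**Working it through.** **1. Days collected but not counted.** Inputs: collection to Day 30 (protocol 12.4.1); TEAE limit for SAEs and deaths Day 14 (protocol 15.4.2.1, SAP 7.4.2); DEAE limit L, the day of the last withdrawal visit. For L up to 30:

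uncounted days = 30 − max(14, L)

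| Subject not entering the extension | Uncounted days | Share of 30 |
|---|---|---|
| Last visit on target, L = 21 | 30 − 21 = 9 (Days 22–30) | 30% |
| Last visit at the window edges, L = 22 or 20 | 8 or 10 | 27% or 33% |
| No withdrawal visit or contact | 30 − 14 = 16 (Days 15–30) | 53% |
| Unscheduled visit or later contact at L > 21 | 30 − L, below 9 | below 30% |

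The documents do not settle whether a phone call moves L. The DEAE definition speaks of a visit, while SAP 6.1.1.2 and Table 3 end the withdrawal period at the later of the last visit and the last phone contact.

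**2. Seriousness.** The table of serious AEs and deaths uses TEAEs only, so it stops at Day 14 for every subject not entering the extension. A serious event between Day 15 and L is a DEAE, but no DEAE table named in the SAP shows it as serious.

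**3. Subjects to whom this can apply.** The sample-size section inflates 96 to 160 per arm. The allowance is 160 − 96 = 64 per arm (64/160 = 40%) who discontinue. They cannot enter the extension, which requires completing 12 weeks. Completers who decline it add to this. These are subjects within scope, not events.

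**4. Interval denominators.** On the Day 0 scale, visits fall on Days 7 and 14.

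- Last visit Day 7: duration = 7 + 1 = 8, which meets the lower bound of 8–14.
- Last visit Day 14: duration = 14 + 1 = 15, which meets the lower bound of ≥15.

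If AE onset is counted from Day 0, such a subject has no follow-up in the new interval. If onset also carries the + 1, there is one day. The label 1–7 fits the Day 0 scale: a DEAE must start after the last-dose day, so the earliest onset is Day 1 there but day 2 with the + 1.

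**5. Illustration of dilution.** Let s be the share of the printed denominator last seen on Day 7 (or Day 14), with no events counted for them in the next interval.

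shown rate = true rate × (1 − s)

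For a true rate of 10%: s = 10% gives 10% × 0.9 = 9%, and s = 20% gives 10% × 0.8 = 8%. Both the 10% rate and the values of s are assumptions; neither is in the documents.

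**The case against.** The best defence is that a reporting window and a tabulation window serve different purposes. Protocol 12.4.1 is a safety-reporting rule. Protocol 15.4.2.1 sets the analysis windows and the SAP copies them. This stands: a reader might infer that the SAP breaks the protocol on the 14-day window, and it does not. But the defence leaves the gap in place, since neither document says that SAEs collected later are meant to be reported by listing only.

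Four further points have weight.

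- **Nothing is lost from the record.** SAP 7.4.2 lists deaths, SAEs and all AEs, whether treatment-emergent or not. The gap is in by-arm counts only.
- **Day 21 ± 1 is the planned end, not a ceiling.** Unscheduled visits, and under the SAP's end-of-study definition phone contacts, can extend it. Table 6.2 has a window from Day 25 onward. The modified withdrawal population (SAP 6.1.9) also brings in some subjects who never enter the withdrawal period, but only for events known by their last visit.
- **Late ascertainment is weaker.** No visit is scheduled after Day 21 ± 1. Protocol 12.4.1 also asks for spontaneous reports of possibly related SAEs once participation ends, which overlaps its own 30-day rule. A 30-day count therefore needs a caveat.
- **Events may be few.** Protocol 4.2 reports one SAE and no deaths in the previous BED study.

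On the denominator, SAP 7.4.2 does not say how onset day is counted, and partial follow-up within an interval is inherent in this kind of table. Both are fair, hence the wording of at most one day. The specific problem is that the + 1 moves the cut-off so that subjects leaving at on-target visits fall just inside the next interval.

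**Conclusion.** The point holds for subjects who do not enter the extension. SAEs and deaths after both Day 14 and the last withdrawal visit or contact, up to Day 30, are collected and listed but enter no by-arm count. That is about 9 of 30 days for full attenders and 16 of 30 for those with no withdrawal visit or contact. These are days, not events; the documents give no late SAE rate. The missing serious DEAE table is a departure from protocol 15.4.2.1 that SAP Section 4 does not declare, although the quoted table rule mentions SAEs and may have been meant to cover it.

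The denominator error is real but small. It dilutes the 8–14 and ≥15 day rates by an amount that depends on how many subjects leave at the Day 7 and Day 14 visits, and the 8–9% figure is illustrative only.

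One stronger reading should not be drawn: that 14 days is too short for the drug's elimination. Protocol 4.2 gives half-lives of 47.1 to 77.0 hours. Five half-lives run from 235.5 h (9.8 days) to 385 h (16.0 days), so only the upper part of the range passes Day 14, and neither document sets a half-life rule.

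Extension entrants are outside the point. I assume that their later SAEs are counted in the extension study, which these documents do not state. The efficacy analyses are unaffected. This should be corrected before database lock, but it does not threaten the trial.

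**What to change.** 1. In protocol 15.4.2.1 and SAP 6.1.11.4.1 and 7.4.2, tabulate SAEs and deaths by arm through Day 30 for subjects not entering the extension. Either extend the SAE and death cut-off, or add a 30-day count beside the 14-day TEAE table. The second option leaves the TEAE definition alone.
2. Add a table note that ascertainment after the last visit relies on site reports, and reconcile the 30-day and end-of-participation statements in protocol 12.4.1.
3. Restore the serious DEAE table in SAP 7.4.2.
4. In SAP 7.4.2, remove the + 1 from withdrawal duration, count AE onset from the same Day 0, and end follow-up at the later of the last visit and the last phone contact, as in SAP 6.1.1.2. Sites already record AEs on those calls (protocol 11.8.10).

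The cost is wording and table programming; no new data are collected. The downside is that a few later SAEs, possibly unrelated and less completely ascertained, enter the counts.

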During the study and prior to database lock, the treatment assignments for all subjects are provided to the Bioanalytical Contract Research Organization (CRO) to facilitate plasma PK sample handling and analysis. No PK samples are analyzed for placebo subjects.

Protocol and IRT Amendment for Stratification Factor of Region

For this US study, there is no concern of ‘region’ difference for treatment effect. Sponsor’s initial intention of including stratification factor of region was to provide an optimization approach to ensure a balanced treatment assignment within each region. It should be noted that stratification by region was not implemented in study SEP360-221, which is also a US study with a similar study design.

The study team noticed on July 20, 2017 that the stratification by region was not implemented as planned, ie, the initiated sites in IRT were linked to incorrect regions (See [Section 6.1.5.1](#) for details). As of July 20, 2017, among 50 planned sites of this study, a total of 44 sites were screening subjects; and 137 subjects from 35 sites had already been randomized. Due to the ‘random’ nature of the incorrect assignment of region according to the root cause of this incident, the study team decided to remove stratification criteria related to ‘region’ to minimize the impact of this mistake. Stratification criteria were amended in study protocol V3.00 and randomization is to be balanced using only permuted blocks with baseline number of binge eating days per

321

week (3 – 4 binge eating days per week, > 4 binge eating days per week).

4. Changes in Planned Analyses

There is not any change made in this SAP from the analyses planned in the protocol.

5. Efficacy and Safety Variables

[Section 6.1.2](#) provides definitions of DB Baseline and Withdrawal Baseline. For the sake of simplicity, hereafter, Baseline and DB Baseline will be used in an interchangeable way.

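### SAP 7.4.2 drops the protocol's by-arm summary of serious discontinuation-emergent AEs without declaring it, so no by-arm table isolates serious events that began after the last dose

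*SAP*

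**What the plan says.** Protocol 15.4.2.1 (Adverse Events) defines a DEAE as an AE starting after the last dose, up to the last visit of the withdrawal period. It then commits to this summary: "The overall incidence of DEAEs and serious DEAEs will be summarized by treatment group". A further sentence plans DEAEs, without a seriousness split, by system organ class (SOC) and preferred term (PT).

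SAP 7.4.2 keeps the DEAE definition. Its table list starts "The overall incidence of DEAEs, DEAEs by SOC and PT" and adds DEAEs by PT, all by treatment group on the modified withdrawal population. One more table follows: "incidence of DEAEs by SOC and PT will be also summarized using time intervals", with withdrawal-duration categories of 1-7, 8-14 and 15 or more days. No item refers to serious DEAEs.

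Earlier in SAP 7.4.2, just before the overall-incidence list that contains the serious-AE row, there is a shorthand: "For sake of simplicity, hereafter TEAE is referred as AE in this section".

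SAP Section 4 (Changes in Planned Analyses) reads: "There is not any change made in this SAP from the analyses planned in the protocol".

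**The concern.** The two documents give different lists of DEAE tables, and the SAP says that they do not differ. The missing item is the only summary in either document that would count, by arm, the subjects with a serious event starting after the drug was stopped. SAP 7.4.1 places withdrawal-period AEs, together with CSSA and DESS, among the data for assessing physical dependence and withdrawal symptoms. Seriousness is a basic attribute of those events.

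If the omission stands, the study report will contain a by-arm serious-event count that mixes on-drug and post-drug onset, and by-arm post-drug tables that do not show seriousness. Anyone wanting the protocol's number would have to build it from listings. Under SAP Section 1, a table added after database lock would have to be identified in the study report as supplementary, although the protocol had pre-specified it.

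**Working it through.** No sample size, power or error rate is involved. The check is a comparison of the two table lists, with one piece of window arithmetic.

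**Inputs**
- Protocol 15.4.2.1: overall DEAEs, overall serious DEAEs, DEAEs by SOC and PT.
- SAP 7.4.2: overall DEAEs, DEAEs by SOC and PT, DEAEs by PT, DEAEs by SOC and PT by withdrawal-duration interval.
- Treatment-emergent (TEAE) window after the last dose for subjects not entering the extension: 7 days for AEs, 14 days for serious AEs and deaths (SAP 7.4.2; protocol 15.4.2.1 has the same windows).
- DEAE window: after the last dose day to the last withdrawal visit.
- Withdrawal period: Day 85 to Day 105 (protocol 7.1).

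**Step 1: the lists.** Protocol list minus SAP list leaves one item, overall serious DEAEs. The SAP adds the PT and interval tables, neither of which is split by seriousness.

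**Step 2: what the serious-AE row means.** Because of the shorthand ("hereafter TEAE is referred as AE in this section"), the serious-AE row in the SAP's overall-incidence list counts serious TEAEs.

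**Step 3: the windows.** Length of the withdrawal period = 105 - 85 + 1 = 21 days. Part covered by the serious TEAE window = 14 days. Remainder = 21 - 14 = 7 days (days 15-21, plus the 1-day visit allowance).

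**Step 4: where a serious event is counted by arm**

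| Onset | SAP serious TEAE row | SAP DEAE tables | Protocol serious DEAE summary |
|---|---|---|---|
| First dose to last dose | Yes | No | No |
| Days 1-14 after last dose | Yes, pooled with the row above | Yes, seriousness not shown | Yes |
| Day 15 to last withdrawal visit | No | Yes, seriousness not shown | Yes |

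Only the last column separates post-drug serious events from the rest, and the SAP omits that column.

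**Step 5: who is affected.** Under SAP 6.1.1.2, subjects who enter the extension have no withdrawal-period analyses. The documents do not say how many will stay out of it. The sample-size section plans for 96 of 160 subjects per arm after allowing for discontinuation, that is 160 - 96 = 64 per arm. Early discontinuers are asked to complete the withdrawal period, as are completers who do not enter the extension. The 64 is a planning allowance, not a forecast of the withdrawal population.

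**The case against.** The best defence is the SAP's scope sentence: "Table summary of overall AEs (and SAEs) will be limited to TEAEs and DEAEs". It stands before the TEAE shorthand and so is not narrowed by it, and it can be read as keeping DEAEs within the SAE tables. The protocol, however, has nearly the same sentence ("The summary of overall AEs (and SAEs) will be limited to AEs and DEAEs") and still names serious DEAEs as a separate summary. The sentence sets limits on the tables; it does not specify one.

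The second defence is the listings, and much of it stands. SAP 7.4.2 provides listings of deaths, SAEs and all AEs whatever their treatment-emergent status, and SAP Section 7 says listings are in general sorted by randomized group. With few events, a by-arm count could be made by hand. What a listing does not give is an incidence with a denominator. The sort order may also differ from the grouping that SAP 6.1.9 prescribes for withdrawal safety data, which is actual treatment: a subject randomized to 6 mg but never titrated counts as 4 mg.

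Several stronger readings are tempting, and the documents do not support them:
- A reader might infer that a table is the only way to see these events by arm. The listings show otherwise.
- A reader might infer that the abrupt-discontinuation objective is left unmet. Protocol 5.3 ties that objective to CSSA, DESS, HAM-A and MADRS, and SAP 7.4.6 summarizes all four. AE reports belong to the general safety objective.
- A reader might infer that the protocol promised serious DEAEs by SOC and PT. It promises only their overall incidence.
- A reader might see the 14-day serious window as a SAP change. It is the protocol's own definition, and post-drug events within it are also counted in the DEAE tables, only without a seriousness label.

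**Conclusion.** The point holds as an undeclared drop of one pre-specified safety summary. The SAP's table list conflicts with protocol 15.4.2.1, and the statement in SAP Section 4 is wrong on this item. As written, no by-arm table isolates serious events with onset after the last dose. Those starting more than 14 days after it are in no by-arm serious-event table at all.

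The size is small. The omission affects only subjects who do not enter the extension, the summary is descriptive, and no efficacy result or error rate depends on it. Counts are likely to be low: protocol 4.2 reports one SAE in the earlier BED study, and I assume rates of that order here. No data are lost, since every serious event remains in the listings.

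The conclusion rests on reading the SAP's DEAE list as complete and on applying the TEAE shorthand to the rest of the section as it says.

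**What to change.** In SAP 7.4.2, add serious DEAEs to the overall-incidence sentence, by treatment group and on the modified withdrawal population already used for the other DEAE tables. That population is defined in the SAP and not in the protocol, so the SAP should name it for this table. A table of serious DEAEs by SOC and PT is optional and goes beyond the protocol's commitment.

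If the sponsor prefers not to produce the summary, SAP Section 4 should declare its removal and give the reason.

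In the same edit, correct the cross-reference in the DEAE paragraph: it sends the reader to Section 6.1.7 (region groups), whereas the modified withdrawal population is defined in Section 6.1.9.

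The cost is one phrase and one table shell before database lock, with no new data collection.
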